Health condition(s) or problem(s) studied	Self-harm
Intervention(s)	Intervention: smartphone-assisted Problem-Solving Therapy (PST)

World Health Organization Trial Registration Data Set Items

DATA CATEGORY	INFORMATION
	Control: standard clinical care
Key inclusion and exclusion criteria	Ages eligible for study: ≥18 years Sexes eligible for study: Male Accepts healthy volunteers: No Inclusion criteria: adult patient (≥ 18 years); patient identifies as male, patient presents to Emergency Department for an index episode of intentional self-harm at an eligible Emergency Departments in Ontario, Canada. Exclusion criteria: patient presents to an eligible Emergency Department for a reason other than intentional self-harm.
Study type	Interventional Allocation: randomized, unbalanced Intervention model: parallel assignment Masking: none Primary purpose: prevention
Date of first enrolment	Pending
Target sample size	25 hospitals; anticipated total sample size of approximately 2,000 men
Recruitment status	Active, not yet recruiting
Primary outcome(s)	Composite measure of suicides and/or proportion of re-presentations to any Emergency Department in Ontario for intentional self-harm
Key secondary outcomes	Within one year of enrollment:
	• Number of suicides;
	• Proportion of self-harm re-presentations to any

DATA CATEGORY	INFORMATION
	Emergency Department in Ontario;
	• Proportion of re-presentations for any reason to any Emergency Department in Ontario;
	• Proportion of hospital admissions for any reason to any hospital in Ontario;
	• Length of stay at any hospital in Ontario for any reason;
	• Proportion of hospital outpatient appointments for any reason at any hospital in Ontario;
	• Number of deaths (mortality rate), for reasons other than suicide and undetermined deaths;
	• Proportion of primary care visits, defined as any visit to a general practitioner;
	• Total health care costs for the treatment of self-harm;
	• Physician costs for the treatment of self-harm;
	• Emergency Department costs for the treatment of self-harm;
	• Hospitalization costs for the treatment of self-harm;
	• Other costs related to the treatment of self-harm.

Table of Contents

1.	FUNDI	NG	8
2.	ROLES	AND RESPONSIBILITIES	8
2	.1. Contr	ibutorship	8
	2.1.1.	Author's Contributions	9
	2.1.2.	Sponsor contact information	9
2	.2. Com	nittees	9
	2.2.1.	Principal Investigator and co-Principal Investigator:	9
	2.2.2.	Steering Committee (refer to title page for membership)	9

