Self-harm has a strong association with suicide: 1.6% of people presenting to Emergency Departments with self-harm will die by suicide within one year (95% confidence interval 1.2 to 2.1%), with the incidence rate being almost double in men compared to women (2.7% vs 1.2%) [8]. Approximately four percent of individuals who have presented to the Emergency Department for the treatment of self-harm die by suicide within five years of their index presentation [8]. This risk is more than 50 times greater than the general population rate and is associated with a 40-year reduction in average life expectancy [8]. A recent population-based cohort study investigating administrative datasets in the province of Ontario discovered that: "all-cause mortality following a first episode of self-poisoning was 1,107 per 100,000 person-years...[with] nearly half of all deaths being suicides, accidents or [of] undetermined intent"[9].

Presentation to the Emergency Department with self-harm is a major identifiable risk factor for suicide, with at least one quarter of deaths by suicide being preceded by a hospital visit due to non-fatal self-harm in the previous year [10-11]. As such, it is likely that any reduction in the repetition of self-harm will be mirrored by a decline in subsequent deaths by suicide. The Canadian Association for Suicide Prevention (CASP) blueprint for a national suicide prevention strategy has also identified people who have attended hospital because of non-fatal self-harm as a high risk group to target in order to prevent suicide [12]. Mortality from non-suicidal causes is also high for those who self-harm, with significantly more than the expected numbers of deaths from natural causes and from accidents [13]. These premature deaths are greatly over-represented among young people and the potential years of life lost in the community are many.

Individuals who self-harm are frequent users of health and social services [14]. Approximately 10% of those who present in an Emergency Department following self-harm will engage in repeat self-harm in the following month and up to 27% after six months [15]. Recurrent self-harm is associated with significant distress and many unresolved interpersonal problems [16].

Why Focus on Men?

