3.3.2. Secondary Hypotheses and Objectives

The key secondary objectives are to determine, compared to usual care, whether the provision of a service that delivers smartphone-assisted PST specifically designed for men who present to the Emergency Department with self-harm, results in:

- 1. Lower suicide rates;
- 2. Fewer contacts with any Emergency Departments in Ontario for the repetition of self-harm;
- 3. Fewer contacts with any Emergency Department in Ontario for any reason;
- 4. Fewer admissions to hospital for any reason;
- 5. Fewer outpatient appointments for any reason at any hospital in Ontario;
- 6. Lower mortality rates, not related to suicide;
- 7. Lower use of primary care services (defined by contact with a family physician); and/or
- 8. Decreased costs to the health care system, including physician, hospitalization, Emergency Department, and other costs.

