4.3.3. Statistical Methods

Outcomes

The unit of analysis will be the individual patient. To evaluate the effectiveness of the complex intervention at population-level (primary trial analysis), all outcomes will be obtained from ICES, regardless of whether men received or participated in the study therapy. Dichotomous primary and secondary outcomes will be described, by arm, using frequencies and percentages. The primary composite outcome as well as its individual components (completed suicides and re-presentations within 1 year) will be compared between the intervention and control sites using generalized linear mixed effects regression, accounting for the pre-and post-intervention measures using repeated cross-sectional analysis [51]. Differences between the arms will be expressed as absolute and relative differences in proportions, together with 95% confidence intervals. Models will account for clustering at the Emergency Department level and over time using random effects. Cluster level covariates for factors used in the allocation procedure, namely urban/rural, onsite psychiatric service, and size will be included in regression models. Additional analyses will adjust for individual prognostic variables including age, ethnicity, pre-specified comorbidities (such as previous hospitalizations for substance use), and repeat as compared with first-time presentations for self-harm.

All binary secondary outcomes (representation to the ED for any reason, admission to hospital for any reason, and mortality for any reason) will be analyzed as described for the primary outcome. Length of hospital stay for any reason, number of hospital outpatient appointments, number of primary care appointments and cost data will be analyzed as described for the primary outcome, that is, using generalized linear mixed effects regression, but with either the Poisson or negative binomial distribution and using the log link function. Differences between the arms will be expressed as rate ratios together with 95% confidence intervals.

Additional subgroup analyses will be carried out for the following subgroups: first time presentations of self-harm compared to repeat presentations; Francophone versus Anglophone; men with substance abuse disorders versus no substance abuse disorder; and rural versus urban residence.

Health Economic Evaluation

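### Objectives 3 and 4 ask about fewer ED contacts and fewer admissions, but the analysis compares only the proportion of men with any; a rate analysis should be added, and the outcome list reconciled with Section 4.3.3

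*Protocol*

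**What the plan says.** Protocol Section 3.3.2 words objective 3 as "Fewer contacts with any Emergency Department in Ontario for any reason" and objective 4 as "Fewer admissions to hospital for any reason". Both are statements about volume.

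The WHO Trial Registration Data Set table at the front of the protocol lists the matching outcomes as proportions: "Proportion of re-presentations for any reason to any" ED in Ontario, and "Proportion of hospital admissions for any reason to any hospital in Ontario".

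Section 4.3.3 confirms the any-versus-none reading. It names "All binary secondary outcomes (representation to the ED for any reason, admission to hospital for any reason" and mortality together as binary, and analyses them like the primary outcome, with absolute and relative differences in proportions.

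The next sentences of Section 4.3.3 treat neighbouring utilisation outcomes differently. Length of stay, number of outpatient appointments, number of primary care appointments and costs get Poisson or negative binomial mixed models, reported as rate ratios. The registration table nevertheless lists outpatient appointments as a proportion and primary care as "Proportion of primary care visits, defined as any visit to a general practitioner". No count or rate analysis of ED contacts or admissions is stated.

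**The concern.** The stated question and the fixed outcome differ for two secondary objectives. Under any-versus-none, a man who goes from ten ED visits in the year to two counts the same before and after. The introduction says "Individuals who self-harm are frequent users of health and social services", which makes repeat contacts a plausible place for an effect to appear.

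At stake is a null result on ED use or admissions when the number of contacts, and their cost, has fallen. ED and hospitalization costs do carry volume, so the report could show a fall in cost beside an unchanged utilisation outcome, with no estimate of the change in contacts to connect them.

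Separately, the registration table and Section 4.3.3 disagree on what is measured for outpatient and primary care use (objectives 5 and 7).

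**Working it through.** **1. Wording side by side**

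| Outcome | Section 3.3.2 | Registration table | Section 4.3.3 |
|---|---|---|---|
| ED, any reason (obj. 3) | fewer contacts | proportion | binary |
| Admission, any reason (obj. 4) | fewer admissions | proportion | binary |
| Outpatient (obj. 5) | fewer appointments | proportion | number, rate ratio |
| Primary care (obj. 7) | lower use | proportion | number, rate ratio |

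The mismatch for objectives 3 and 4, and the contradiction for 5 and 7, need no assumed figure.

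**2. The plan's own power figure**

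Inputs from Section 4.1.5: ICC 0.01, 80 men per cluster, coefficient of variation 0.30, 15 control and 10 intervention clusters (1,200 and 800 men). Two-sided alpha of 0.05 is assumed.

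Design effect = 1 + ((1 + 0.3²) × 80 − 1) × 0.01 = 1.862.

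For 13% versus 7.7%, a post-period comparison of two proportions gives power of 79.2% (stated: 80%). The design effect is therefore a fair basis for what follows, on the assumption that it also applies to these secondary outcomes, binary or count.

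**3. What any-versus-none retains of a fall in contacts**

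The documents give no distribution of contacts. Assume negative binomial counts with mean m and shape k, and a uniform 25% fall in the rate.

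- Proportion with any: P = 1 − (k/(k+m))^k.
- Binary z: (P₁ − P₂) / √(P₁(1−P₁)/1200 + P₂(1−P₂)/800).
- Count z: |ln 0.75| / √((1/m + 1/k)/1200 + (1/(0.75m) + 1/k)/800).
- After clustering: divide z by √1.862 = 1.365; power ≈ Φ(z − 1.96).

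Example, m = 3 and k = 0.7: P₁ = 68.8%, P₂ = 63.5%, ratio 0.922. Binary z = 0.0536/0.02165 = 2.47, or 1.81 after clustering. Count z = 0.2877/0.0617 = 4.66, or 3.42 after clustering.

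| m, k | Proportion with any | Ratio | z before clustering, binary / count | z after clustering, binary / count | Power, binary / count |
|---|---|---|---|---|---|
| 2, 0.5 | 55.3% to 50.0% | 0.904 | 2.32 / 3.91 | 1.70 / 2.87 | 40% / 82% |
| 3, 0.7 | 68.8% to 63.5% | 0.922 | 2.47 / 4.66 | 1.81 / 3.42 | 44% / 93% |
| 4, 1.0 | 80.0% to 75.0% | 0.938 | 2.61 / 5.53 | 1.91 / 4.05 | 48% / 98% |
| 6, 1.0 | 85.7% to 81.8% | 0.955 | 2.30 / 5.75 | 1.68 / 4.22 | 39% / 99% |

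A 25% fall in contacts thus appears as a relative fall of 4.5% to 9.6%. If the fall occurs only among men who still have at least one contact, the ratio is exactly 1.00.

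**4. Lower contact rates**

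- Mean 0.5 (assumed, possible for admissions), k 0.5 to 1.0: ratio 0.83 to 0.82. Before clustering, z is 2.4 to 2.9 binary and 3.0 to 3.4 count. The loss is modest.
- Mean 0.16, k 0.7, which gives 13.4% with any, close to the 13% repetition rate in Section 4.1.5: 13.4% to 10.5%, ratio 0.78 against a true 0.75. Before clustering, z is 2.01 binary and 2.11 count. Almost nothing is lost.

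A second set of assumptions (30% fall, k 0.3 to 2) shows the same pattern: ratio 0.72 to 0.75 at a mean of 0.16, and 0.90 to 0.95 at means of 3 to 5.

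**The case against.** Any-versus-none is a legitimate estimand and is robust to a few extreme users. It answers whether fewer men use the ED or are admitted. Length of stay and separate ED and hospitalization costs, modelled with rate ratios, carry some of the volume. The remark that these men are frequent users comes with no figure for ED visits or admissions, and an analysis plan could add a supportive count model. Most of this stands: it limits the size of the point, but the wording mismatch remains. The protocol itself fixes the outcome type for objectives 3 and 4, so this is not merely detail left to a later plan.

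Three stronger readings are tempting, and the documents do not support them.

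- **That objective 2 is affected in the same way.** It too is worded as a count: "Fewer contacts with any Emergency Departments in Ontario for the repetition of self-harm". But near 13% repetition the binary measure keeps nearly all of a uniform effect. The primary hypothesis uses similar wording with a binary composite, and this outcome is a component of that composite.
- **That the review of psychosocial interventions cited in Section 3.1.1 argues for counts.** It reports fewer participants repeating self-harm (OR 0.70, 95% CI 0.55 to 0.88) and no reduction in frequency (mean difference −0.21, −0.68 to 0.26). For self-harm, that does not favour replacing the proportion.
- **That objectives 3 and 4 cannot be answered, or that an effect would be largely invisible.** Part of the question is answered, and the loss depends on contact rates the protocol does not give.

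**Conclusion.** The point holds for objectives 3 and 4. They ask about numbers of contacts and admissions, while the outcomes are fixed as the proportion of men with any. The registration table and Section 4.3.3 also contradict each other on outpatient and primary care use. Both are visible on the page.

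The statistical cost is conditional. It is substantial if ED contacts average 2 to 6 per man-year and modest if the mean is nearer 0.5, as it may be for admissions. These figures assume negative binomial counts, a uniform 25% fall, the Section 4.1.5 design effect for both types of outcome, and a post-period normal approximation. They show what could be lost, not what will be.

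The primary outcome is untouched. This is a cheap improvement to two secondary outcomes, together with a correction of inconsistent wording.

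**What to change.** - In Section 4.3.3, for ED contacts for any reason and admissions for any reason, add a rate analysis with the negative binomial mixed model already available for appointments. Use time alive in the follow-up year as the offset, and report rate ratios beside the any-versus-none proportions.
- In the registration table, add the matching rate outcomes for these two, and change the outpatient and primary care entries from proportion to number so that they agree with Section 4.3.3.
- Leave the primary composite and its self-harm re-presentation component (objective 2) binary.

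The cost is two more models on data already held at ICES, plus protocol and registry wording. The downside is that a few very high users will influence the rate ratios, which is a reason to keep the proportions alongside.

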3.4. Trial Design

This is a pragmatic, multicentre pre- and post-design cluster RCT comparing the offer of a service that delivers smartphone-assisted PST to usual care, in men who present to the Emergency Department with self-harm. We have chosen a cluster randomized design because we are testing the introduction of a service for suicidal men that addresses both the need to manage the transition from the Emergency Department to outpatient care and the provision of care specifically designed for men who have intentionally self-harmed.

By randomizing entire sites with a waiver of informed consent for data collection with inclusion of all eligible men using routinely collected data, external validity of the study is maximized, in comparison to an individually randomized trial with a requirement to seek informed consent (refer to Section 5.3 Consent).

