4.1.4. Outcomes

The primary outcome measure will be a composite of the incidence of suicides and/or re-presentations to any Emergency Department in Ontario for self-harm in the year after the index episode of self-harm. The incidence of suicide and re-representation to Emergency Department will be measured using ICD-10-CM codes T360-T50992, T510-T6592, T71112-T71232, X71-X83 (refer to Appendix A for full list of codes and descriptors) [46]. Individuals who died by suicide will be identified in ICES using the Vital Statistics - Death Database. A potential problem with the outcome measures in this trial is that the intervention may also change help-seeking behaviour. That is, men may seek out healthcare that they would not have in the past, which may lead to an increase in re-presentations to the Emergency Department for patients in the intervention group. In order to explore changes to health-related help-seeking, we will also collect data on primary care and hospital outpatient care not driven by emergencies through ICES. This will be measured in ICES, using the Ontario Health Insurance Plan (OHIP) Claims Database and National Ambulatory Care Reporting System Metadata (NACRS). We will also address this through a sub-study of smartphone-assisted PST.

The secondary outcome measures will include total number of suicides; representations to any Emergency Department in Ontario for the repetition of self-harm; representations to any Emergency Department in Ontario for any reason; other health system use including use of primary care and hospital outpatient appointments; mortality not related to suicide; and, health system costs within one year which will inform an economic analysis. All outcomes will be identified and measured using routinely collected data housed at ICES. Men who present with intentional self-harm in the study Emergency Departments will be identified from ICES administrative health data.

	Justification	Data Source	Data Collection Period
Primary Outcome Va	riable (composite outco	ome variable)	
Death by Suicide	To assess the clinical	ORGD, NACRS	Baseline; 12 months
and/or re-	impact of the	(ICES)	
presentation to any	provision of a		
Emergency	smartphone-assisted		
Department in	PST service.		
Ontario for Self-harm			
Secondary Outcomes	Secondary Outcomes		
Death by Suicide	To assess the clinical	ORGD (ICES)	Baseline; 12 months
	impact of the		
	provision of a		
	smartphone-assisted		
	PST service.		

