Re-presentation to	To assess the clinical	NACRS (ICES)	Baseline; 12 months
any Emergency	impact of the		
Department in	provision of a		
Ontario for Self-harm	smartphone-assisted		

Table 2. Outcome Measures

	PST service.		
Re-presentation to any Emergency Department for any reason	To assess the clinical impact of the provision of a smartphone-assisted PST service.	NACRS (ICES)	Baseline; 12 months
Admission to any hospital in Ontario for any reason	To assess the clinical impact of the provision of a smartphone-assisted PST service.	NACRS (ICES)	Baseline; 12 months
Hospital outpatient appointments in Ontario for any reason	To assess the clinical impact of the provision of a smartphone-assisted PST service.	OHIP (ICES)	Baseline; 12 months
Primary care appointments	To assess the clinical impact of the provision of a smartphone-assisted PST service.	OHIP (ICES)	Baseline; 12 months
Mortality for reasons other than suicide	To assess the clinical impact of the provision of a smartphone-assisted PST service.	ORGD (ICES)	Baseline; 12 months
Total Health Care Costs	To assess the economic impact of the provision of a smartphone-assisted PST service.	OHIP, DAD, NACRS, NRS, CCRS, OMHRS, ODB, ADP (ICES)	Baseline; 12 months
Physician Health Care Costs	To assess the economic impact of the provision of a smartphone-assisted PST service.	OHIP (ICES)	Baseline; 12 months
Emergency Department Health Care Costs	To assess the economic impact of the provision of a smartphone-assisted PST service.	NACRS (ICES)	Baseline; 12 months
Hospitalization Health Care Costs	To assess the economic impact of the provision of a smartphone-assisted PST service.	DAD (ICES)	Baseline; 12 months
Other Health Care Costs	To assess the economic impact of the provision of a	NRS, CCRS, OMHRS, ODB, ADP (ICES)	Baseline; 12 months

	smartphone-assisted		
	PST service.		
Prognostic outcome n	neasures		
Age	To assess differences	RPDB (ICES)	Baseline
	between subgroups.		
Previous	To assess differences	NACRS (ICES)	Baseline
hospitalization for	between subgroups.		
self-harm			
Previous	To assess differences	NACRS (ICES)*	Baseline
hospitalization for	between subgroups.		
substance use			

* Appendix B for list of ICD-10-CM codes.

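### The main models for the count and cost secondary outcomes omit each man's own prior-year value of the same measure, a cheap source of precision and of some protection against case-mix change

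*Protocol*

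**What the plan says.** Protocol section 4.3.3 models length of hospital stay in the same way as the other counts and the costs: "number of hospital outpatient appointments, number of primary care appointments and cost data will be analyzed as described for the primary outcome". The only change is a Poisson or negative binomial distribution with a log link. The inherited model has these parts:

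- Pre- and post-intervention data enter by "accounting for the pre-and post-intervention measures using repeated cross-sectional analysis".
- Random effects account for clustering by Emergency Department and over time.
- The covariates are at site level: "Cluster level covariates for factors used in the allocation procedure, namely urban/rural, onsite psychiatric service, and size will be included in regression models".

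Individual characteristics come in separately: "Additional analyses will adjust for individual prognostic variables including age, ethnicity, pre-specified comorbidities". Earlier hospital stays for substance use are given as an example of the comorbidities, and first versus repeat self-harm presentation completes the list. A man's earlier outpatient visits, primary care visits, length of stay or costs are not named.

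On data, section 4.1.4 says: "All outcomes will be identified and measured using routinely collected data housed at ICES". Table 2 there also takes previous hospitalizations for self-harm and for substance use from NACRS at baseline.

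**The concern.** A repeated cross-section compares different men at the same site before and after. It shows whether a site's patients were heavy users on average. It does not show whether a particular man in the post-period was one. Two things follow for the count and cost outcomes.

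- **Precision.** Any part of the variation between men that their own earlier use or cost would explain stays in the residual and widens the interval for the rate ratio.
- **Case mix.** The pre-period cannot remove a change in who is captured if that change happens in one arm only. The protocol leaves a route for this. Sections 4.1.3 and 4.3.1 give intervention sites training on recognising and managing self-harm. Section 4.2.2 keeps control sites unaware of the study. Section 4.1.2 defines the cohort by recorded codes. Section 3.1.1 reports that self-harm is under-detected and inconsistently recorded. Better identification at the 10 intervention sites, in the post-period only, could alter the mix of heavy and light users there.

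Secondary objectives 5, 7 and 8 (outpatient care, primary care and costs) rest on these outcomes. Section 4.1.4 also relies on the primary care and outpatient data to explore whether help-seeking changed, which bears on how the primary result is read.

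**Working it through.** **The plan's own figure.** The protocol states no power or precision for the count and cost outcomes, so only the primary calculation in section 4.1.5 can be reproduced. With 80 men per site, a cluster-size CV of 0.30 and an ICC of 0.01, the post-period design effect is 1 + ((1 + 0.30²) × 80 − 1) × 0.01 = 1.862. With 10 v 15 sites and two-sided 5% (assumed), 13% v 7.7% gives 79.2% power (pooled z) or 81.9% (unpooled z), which matches the stated 80%. The same method gives 94.0% or 95.5% for the 50% reduction, against a stated 90%. No single variant tried returned both stated figures. The point here depends on neither.

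**Inputs for the gain.**

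- From section 4.1.5, for the primary outcome and borrowed here: m = 80 men per site and period, ICC = 0.01, inter-period correlation c = 0.008.
- Assumed: the correlation r between a man's prior-year and follow-up value, 0.3 to 0.7; a continuous working scale with total variance 1; equal cluster sizes; r explains within-site variance only.

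**Formulas.** The variance of a site mean is v = ICC + (1 − ICC)(1 − r²)/m. Adjusting for the site's pre-period mean (an ANCOVA-type pre/post analysis) gives V = v − c²/v. Number of sites and allocation ratio cancel in the comparison.

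**Without the prior value (r = 0).** v = 0.01 + 0.99/80 = 0.022375, so V = 0.022375 − 0.000064/0.022375 = 0.019515.

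**With it.**

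| r | v | V | V relative to r = 0 | SE reduction |
|---|---|---|---|---|
| 0.3 | 0.021261 | 0.018251 | 0.935 | 3.3% |
| 0.5 | 0.019281 | 0.015962 | 0.818 | 9.6% |
| 0.7 | 0.016311 | 0.012388 | 0.635 | 20.3% |

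**Sensitivity to the assumptions.**

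- Assumed ICC 0.05 and c = 0.04: V at r = 0 is 0.036016. It falls to 0.034493 at r = 0.3 and 0.027513 at r = 0.7, so the SE falls by 2.1% to 12.6%.
- Post-period data only, ICC 0.01: the SE falls by 2.5% (r = 0.3) to 14.6% (r = 0.7).
- Pre/post difference analysis, variance 2(v − c), ICC 0.01: the SE falls by 4.0% to 24.0%.
- If the prior value explained between-site variance in the same proportion, variance would fall by r², that is 9% to 49%. Nothing in the protocol supports assuming this.

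The size of any arm-differential shift in case mix cannot be calculated from the document.

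**The case against.** The strongest reply is that covariates for secondary outcomes commonly belong in the SAP, and that the individual list in section 4.3.3 is open-ended, so prior use could be added later without contradiction. This stands for the additional analyses. It does not settle the main models, for which section 4.3.3 names a specific site-level set and places individual covariates elsewhere. The point concerns that stated choice.

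Three stronger readings are tempting, and the protocol does not support them.

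- A reader might take Table 2's "Baseline; 12 months" to show that a per-man baseline was planned and then left unused. The same entry stands against suicide and other mortality, which no analysed man can have had at his own baseline. It fits the pre-intervention cross-section of the pre/post design. The point does not need it.
- A reader might infer that protection against imbalance is abandoned. Allocation was constrained on four site factors, three of them are in the model, and the pre-period data handle stable site differences. Only a within-site shift that differs by arm remains unaddressed, and the protocol gives no evidence that one will occur.
- A reader might infer that prior use appears nowhere. Earlier hospital stays for substance use and repeat presentation are in the additional analyses. They are related measures, but not the man's own earlier value of the outcome.

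It is also fair that the size of the gain rests on borrowed and assumed figures. At r = 0.3 it is slight.

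**Conclusion.** The point holds as an inexpensive improvement to the main models for length of stay, outpatient appointments, primary care appointments and each cost outcome. It is not an error that invalidates the plan. The gain in standard error is about 3% to 20% for an assumed correlation of 0.3 to 0.7, or 2% to 13% at an assumed ICC of 0.05. It rests on primary-outcome correlations borrowed for other outcomes and on the prior value explaining within-site variance only. Protection against an arm-differential change in case mix would improve, but only for the part that prior use measures.

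The primary analysis is unaffected. No gain is claimed for the binary secondary outcomes, such as any-reason re-presentation or admission, because the calculation does not address them.

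**What to change.** In section 4.3.3, state that the count and cost models will include, besides the site covariates, the man's own value of the same measure in the 12 months ending the day before his index presentation, for example as log(1 + prior value). Define it identically for pre- and post-period men. Keep the model without it as a sensitivity analysis. With a log link, the rate ratio keeps essentially the same meaning after adjustment.

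The cost is a 12-month look-back in the ICES extraction and an indicator for men with under 12 months of prior OHIP coverage. No extra patients or patient contact are needed.
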